The design will be a prospective, open-label, multi-center longitudinal cohort study to assess the short- and long-term safety of FMT as well as the clinical resolution of diarrhea among 150 patients with 3 or more episodes of CDI (defined as 3 unformed stools over 24 hours for 2 consecutive days and either a positive stool test for CDI or pseudomembranes on colonscopy/sigmoidoscopy).²⁶ Subjects will be adult outpatients referred to one of the study centers after at least three recurrent episodes of CDI and previous treatment with at least one 10-day course of oral vancomycin or fidaxomicin. After FMT by colonoscopy/sigmoidoscopy or enema, patients will be followed prospectively and monitored for clinical resolution and adverse events at: 3 days (telephone), 6 weeks (clinical assessment), 6 months (telephone or clinical assessment), and 12 months (telephone or clinical assessment) after FMT. Subjects who recur will be offered a second FMT by colonoscopy with a different donor. Microbiome analysis will be conducted from stool samples at baseline and each of the 4 follow-up intervals.

III. Product Name/Chemical Structure

Fecal Microbiota Preparations

IV. Proposed Indication(s)

Recurrent Clostridium difficile infection

V. Dosage, Route of Administration and Dosing Regimen

V-A Colonoscopic/sigmoidoscopic FMT (FMP250)

Dosage Form: Screened human donor stool,

homogenized, filtered and aliguoted to sterile 250mL

vessels.

Route of Administration: Infusion will occur in the most proximal region of the colon that is technically feasible. The material will be infused through the working channel of the endoscope.

Dosing Regimen: 250 mL x 1 dose. In the event of a clinical non-response (defined in 'Protocol' Section), a repeat single 250 mL dose will occur from a different donor.

V-B Retention Enema FMT (FMP250E)

Dosage Form: Screened human donor stool,

homogenized, filtered

and aliguoted to sterile 250mL

vessels.

Route of Administration: Lubricated enema nozzle will be inserted into rectum and contents expelled into the distal colon with the subject requested to retain material for at minimum 30 minutes.

Dosing Regimen: 250mL x 1 dose. In the event of clinical non-response (defined in 'Protocol' Section), a repeat single 250 mL dose via colonoscopy will occur from a different donor.

4. [RESERVED, CFR 312.23]

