- Immunosuppressant medications
 - Current or recent (<3 months) treatment with anti-neoplastic agents
 - Current or recent (<3 months) treatment with calcineurin inhibitors (tacrolimus, cyclosporine)
 - Current or recent (<3 months) treatment with mycophenolate mofetil
 - Current or recent (<3 months) treatment with monoclonal antibodies to B and T-Cells, anti-TNF, glucocorticoids, antimetabolities (azathioprine, 6-mercaptopurine)
- Neutropenia with absolute neutrophil count (ANC) <0.5 x 10⁹/L
- Active gastroenteritis due to infectious cause other than CDI
- Short gut syndrome
- Colostomy
- Ascites
- End-stage liver disease
- Untreated, in-situ colorectal cancer
- Irritable bowel syndrome
- Inflammatory bowel disease including Crohn's disease and ulcerative colitis
- Microscopic colitis including collagenous colitis and lymphocytic colitis
- Severe food allergy (anaphylaxis) that cannot be confirmed as having been excluded from a donor's diet within the five days prior to donation
- Anorectal disorder/severe rectal sphincter tone abnormality or inability to retain enema material
- Unable or unwilling to tolerate colonoscopy/sigmoidoscopy, colonoscopy prep, or enema for any reason at discretion of MD
- Severe underlying disease that the patient is not expected to survive for the subsequent 12 months at the discretion of the MD.
- Any conditions for which, in opinion of MD, the treatment may pose a health risk

Target enrollment and rationale

The longitudinal cohort sample size (n=150) was chosen to allow recruitment in a suitable time frame. Strong consideration will be given to resubmitting documentation including IND amendment and IRB ammendment for a larger sample size and/or prolonged follow-up at the completion of the study.

III. Design Methodology

IV. Therapeutic Administration: Fecal Microbiota Transplantation Protocol

Donor selection, laboratory screening, and monitoring

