A. Donor Clinical Assessment: OpenBiome utilizes adult, healthy, universal donors who have given informed consent with oversight from Massachusetts Institute of Technology (MIT) IRB/COUHES. Refer to the OpenBiome Master File (BB-MF 15543) for donor selection details. An accompanying authorization letter from OpenBiome can be found in Appendix 1. The OpenBiome Donor Risk Factor Questionnaire (Appendix 2) is detailed elsewhere. Briefly, the Donor Risk Factor Questionnaire is modified from a similar questionnaire developed by the American Association of Blood Banks for blood donors. The stool donor questionnaire is used to exclude potential donors with infectious disease risk factors (eg. high risk sexual behavior, risk factors for variant Creutzfeldt-Jakob disease, high risk travel), medications that may mediate the microbiome, and a wide array of medical conditions that may have a theoretical link the microbiome.

B. Donor Laboratory Screening: Refer to the OpenBiome Master File (BB-MF 15543) for donor laboratory screening details. An accompanying authorization letter from OpenBiome can be found in *Appendix 1*. Briefly, both serologic and stool test are completed on prospective donors. All tests are outsourced to third-party Clinical Laboratory Improvement Amendments (CLIA)-certified testing facilities. As a condition for participation in this program, donors are required to submit written authorization for the disclosure of these test results to the OpenBiome, in compliance with the Health Insurance Portability and Accountability Act (HIPAA).

C. Donor Monitoring: Refer to the OpenBiome Master File (BB-MF 15543) for donor monitoring details. An accompanying authorization letter from OpenBiome can be found in *Appendix 1*. Briefly, the OpenBiome Donor Prospective Health Status Questionnaire (*Appendix 3*) details the routine questions asked before processing of a specimen, with initiation of clinical assessment by the Chief Medical Officer if a positive answer disclosed by a donor.

Subject preparation: determining eligibility, pre-treatment, and special considerations A. Subject Clinical Assessment

1. Potential subjects will undergo a medical interview to determine eligibility for the study and a physical exam will be performed at the screening visit.

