1. Females of childbearing potential will have a urine pregnancy test on the day of enrollment and be excluded if pregnant. 2. Female subjects must not be and should not become pregnant nor breast-feed an infant while in this study. In order to reduce the risk of pregnancy, the subject or her partner should use one or more of the acceptable methods of birth control listed below, regularly and consistently, while enrolled in this study. Acceptable methods of birth control, which will continue throughout the study and for one month after the study, include:

- Approved oral contraceptive/birth control pill
- Intra-uterine device (IUD)
- Hormone implants
- Contraceptive injections (Depo-Provera)
- Barrier method (diaphragm with spermicidal gel or condoms)
- Transdermal contraceptives (birth control patch)
- Vaginal contraceptive ring (birth control rings)
- Sterilization (tubal ligation, hysterectomy or vasectomy)
- Abstinence

3. If subjects become pregnant or suspect that they are pregnant during this study, they will be instructed to immediately inform the study personnel. If subjects become pregnant or suspect that they are pregnant while in this study, a pregnancy test will be performed. If pregnancy is confirmed, they will be withdrawn from the study if FMT therapy has not yet occurred. If FMT has occurred and conception occurs within the study period, the study physician will assist the patient in getting obstetrical care and will follow the progress of the pregnancy. The study physician will request access to subject and/or infant's medical records for up to 8 weeks after delivery.

Preparation and handling of stool for FMT infusion

1. Frozen material will thaw for 4 hours at room temperature. After thawing, material may remain at room temperature for up to 4 hours, or be kept refrigerated/on ice for up to 8 hours.

2. Standard protocol for handling biohazardous material will be employed in order to avoid contamination and risk to healthcare handlers. Sterile microbiological technique will be employed during material transfer periprocedure.

FMT procedure guidelines

1. Colonoscopy/sigmoidoscopy

- The procedure will be completed by a trained gastroenterologist or general surgeon in a standard endoscopy unit.
- Colonoscopy/sigmoidoscopy will be performed under direct visualization, aiming to reach the most proximal part of the colon using safe endoscopic maneuvers and minimal insufflation.

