1. Colonoscopy/sigmoidoscopy: If patients experience clinical non-response and require vancomycin/fidaxomicin within 6 weeks post-FMT, after a 10 day course subject may opt to undergo a second FMT via colonoscopy with an alternate donor at the physician's discretion. Subjects will be followed per protocol for duration of study.

2. Enema: If patients experience clinical non-response and require vancomycin/fidaxomicin within 6 weeks post-FMT, after a 10 day course subject may opt to undergo a second FMT via colonoscopy with an alternate donor at the physician's. Subjects will be followed per protocol for duration of study.

Withdrawal

- 1. All reasons for study withdrawal will be reported.
- 2. Classification of withdrawal:
 - Post-enrollment but pre-FMT
 - Post-FMT but lost to follow-up at:
 - o Day 3
 - o Week 6
 - o Month 6
 - \circ Month 12
 - All reasonable efforts will be exhausted to contact subjects, and data analysis will be based on the last available assessment.
 - Adverse event or serious adverse event mediating withdrawal
 - Rescind informed consent
 - Procedure-related ineligible patients
 - Patients undergoing colonoscopy/sigmoidoscopy and discovered to be ineligible due to newly discovered exclusionary criteria (eg. in-situ colorectal cancer). FMT will not be performed as part of this study and no data will be collected.

V. Study Observations and Measurements

Study Endpoints

Safety Endpoints

Safety will be assessed by short and long-term safety summaries classified into:

- 1. Serious Adverse Events (SAE)
- 2. Adverse Events (AE)
- 3. New medical conditions
- 4. Changes in pre-existing medical conditions

Efficacy Endpoints

Efficacy will be captured through:

- 1. Clinical cure rate of first FMT at 6-week follow-up
 - Colonoscopy
 - Sigmoidoscopy
 - Enema

2. Clinical cure rate of second FMT at 6-week follow-up, in patients with clinical non-response

- Colonoscopy/sigmoidoscopy non-response: Alternate donor FMT by colonoscopy
- Enema non-response: Alternate donor FMT by colonoscopy

Microbiome Endpoints

Sequencing data targeting the composition of the gut microbiome will be used to assess whether there are consistent microbial signatures associated with clinical cure, clinical non-response, or safety endpoints.

Data Collection

Case Report Forms will be utilized to capture and collect data (Appendix 4):

1. Baseline Assessment (Day 0 - Clinical Assessment)

Section 1: Clinical Evaluation

- Study patient identifier
- Date

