- Demographics: Age, sex, race/ethnicity
- Pre-existing medical conditions
- Concomitant medications
- Vital signs including height, weight, calculated body mass index (BMI)
- CDI History, including:
 - o Date of initial CDI diagnosis
 - Number of CDI recurrences since initial diagnosis
 - o Baseline clinical symptoms and severity related to CDI
 - CDI treatments received to date

Section 2: FMT Procedure

- Study patient identifier
- Date
- Description of FMT procedures, including:
 - Route of administration (colonoscopy/sigmoidoscopy or enema)
 - Location in colon where FMT delivered
 - Sedation (if applicable)
 - Prep quality (if applicable)
 - Findings of colonoscopy (if applicable)
- Dose
- Unit ID/Lot# of each treatment
- Expiration Date
- Storage Condition
- FMT retention time (if less than 1 hour)
- Immediate adverse events

2. Short-term assessment I (Day 3 – Telephone Assessment)

- Study patient identifier
- Date
- Any change in baseline clinical symptoms related to CDI
- Assessment of SAEs, including:
 - Any complications related to FMT administration
 - Any potential infectious complications such as transmissible enteric infections, sepsis, peritonitis, or bacteremia
 - Any non-serious newly diagnosed infections (specific organism and body site)

- Any new medical conditions / new medications with associated clinical course
- Any changes in pre-existing medical conditions with associated clinical course
- 3. Short-term assessment II (Week 6 Clinical Assessment)
 - Study patient identifier
 - Date
 - Vital signs including height, weight, calculated body mass index (BMI)
 - Any change in baseline clinical symptoms related to CDI including documentation of clinical cure or clinical non-response
 - Assessment of SAEs, including:
 - Any complications related to FMT administration
 - Any potential infectious complications such as transmissible enteric infections, sepsis, peritonitis, or bacteremia.
 - Any new non-serious diagnosed infections (specific organism and body site)
 - Any new medical conditions / new medications with associated clinical course
 - Any changes in pre-existing medical conditions with associated clinical course

4. Long-term assessment I (Month 6 – Telephone Assessment)

- Study patient identifier
- Date
- Self-reported height and weight, resulting calculated BMI
- Any recurrence of CDI with description of clinical course, including additional treatments received
- Assessment of any new SAEs

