There have been no confirmed infectious complications directly attributable to FMT reported in the literature to date aside from a speculation about a norovirus case although the donor was untested for this.²⁹ There have been two FMT cases of bacteremia, although the strength of the association is unclear, and both patients did well on antibiotic therapy. However, since the process involves infusion of one person's "body fluids" into another person, transmission of an infectious agent or other disease or condition remains a theoretical possibility. From infusion of donor microbiome, the patient/subject could potentially acquire risk factors for chronic diseases such as diabetes or inflammatory bowel disease. Risks will be minimized by a rigorous donor selection process and evaluative studies on stool and blood of the donor to exclude transmission of infectious agents prior to FMT. Subjects will be informed that the treatment or procedure may involve these theoretical risks and additional risks that are currently unforeseeable. There have been reported cases of inflammatory bowel disease flares post-FMT, but it is unclear if this was attributable, and these patients have been excluded from this study. Infusion of fecal material containing a potential agent to which the subject is allergic is also a concern and so patients with a history of severe (anaphylactic) food allergy will be excluded from this study.

VII-C. Potential Risks to Donors

This study also involves individuals (donors) recruited to donate stool for FMT. There are 3 areas of risk to the potential stool donor.

These include:

 Physical risks related to laboratory testing and the stool collection protocol
 Psychological risks related to both revealing and potentially learning sensitive information during donor screening process

3) Risks related to confidentiality and loss of privacy.

OpenBiome volunteer donors will be utilized. In order to exclude donors at high risk of passing infection, a Donor Risk Factor Questionnaire (*Appendix* 2) will be administered. This questionnaire contains sensitive and potentially embarrassing questions

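### The risk section excludes every patient with anaphylactic food allergy, but the eligibility criterion admits some of them and does not clearly require a donor-diet check for each unit given

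*Combined protocol and SAP*

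**What the plan says.** Two current sections give a rule on severe food allergy.

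- **Section 6, VII-B (Potential Risks to Subjects).** After naming infusion of an allergen as a hazard, the text states that "patients with a history of severe (anaphylactic) food allergy will be excluded from this study". No condition is attached.
- **Section 6, II (Exclusion criteria).** The bullet reads "Severe food allergy (anaphylaxis) that cannot be confirmed as having been excluded" from a donor's "diet within the five days prior to donation". The exclusion applies only when that confirmation fails.

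On repeat dosing, Section 3, V-A says that after clinical non-response "a repeat single 250 mL dose will occur from a different donor", and V-B says the same for subjects first treated by enema. Section 6, IV (In the event of clinical non-response) says that "after a 10 day course subject may opt to undergo a second FMT via colonoscopy with an alternate donor".

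On the material, the donors are universal donors. The Donor Monitoring paragraph says that the questionnaire in Appendix 3 "details the routine questions asked before processing of a specimen". The product is stored frozen: "Frozen material will thaw for 4 hours at room temperature". The procedure section of the case report form, as listed under Data Collection, includes "Unit ID/Lot# of each treatment".

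**The concern.** The protocol has two rules for one safety exclusion. A reader of VII-B, such as an ethics committee or the DSMB, would conclude that no patient with anaphylactic food allergy is ever exposed. A site working from the exclusion list could properly enroll one.

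The second issue follows from the first. If such a patient can enter, the safeguard is the diet confirmation, and the criterion speaks of a donor in the singular. It can be read as covering any donor whose material the subject receives, or only the donor of the first unit. On the second reading, a site could enroll a patient on a confirmed first donor and later give a unit from another donor that the protocol text does not require anyone to check.

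What is at stake is subject safety and uniform eligibility across sites. Section 6, VI lists allergic reaction as an example of a material-related adverse event. Under VI-G, a single serious, unexpected event related to the material triggers a safety review with enrollment suspended.

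**Working it through.** The plan gives no figure to reproduce, so the check is a comparison of text plus two counts.

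**Step 1: the two rules applied to the same patient.**

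| Patient with a history of anaphylactic food allergy | Section 6, II | Section 6, VII-B |
|---|---|---|
| Allergen not confirmed absent from the donor's diet | Excluded | Excluded |
| Allergen confirmed absent from the donor's diet | Eligible | Excluded |

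The rules disagree in the second row. Both are current text, and nothing elsewhere in the document reconciles them.

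**Step 2: units and donors per subject.** From Section 3, V: 1 first dose + at most 1 repeat dose = at most 2 units, the second from a different donor. If the first unit is checked at enrollment, at most 2 − 1 = 1 unit per affected subject lacks a clearly stated check.

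**Step 3: does the second-dose text supply the check?**

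- Eligibility is settled at screening, before Day 0. The alternate donor comes into play only later, after non-response.
- Both items under the non-response heading require a 10-day antibiotic course and an alternate donor. Neither mentions donor diet or a renewed eligibility check.
- VII-D (Protection against risk, item 4) makes any patient with recurrence eligible for a second FMT from a different donor, again without a diet condition.
- VI-G bars a second FMT only after a related SAE. That does not help a subject whose first unit was uneventful and whose second contains the allergen.

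**Step 4: is the confirmation recorded?** The FMT Procedure section of the baseline form lists 9 items: identifier, date, procedure description (with 5 sub-items), dose, unit or lot number, expiration date, storage condition, retention time and immediate adverse events. None of the 9 items or 5 sub-items concerns donor diet or an allergen. The protocol's summary of donor monitoring does not mention diet either.

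**Step 5: what could not be checked.** The donor master file, the two donor questionnaires (Appendices 2 and 3), and the pre-enrollment checklist and case report forms (Appendix 4) are not in the text reviewed. Any of them may contain a diet check.

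**The case against.** The strongest reply is that sites have one operative list, the exclusion criteria, and that VII-B merely summarizes it in a narrative about theoretical risks. A site that did follow VII-B would err on the safe side. On the per-unit point, the five-day window is tied to a donation, so the criterion is most naturally read as applying to whatever material the subject receives; checking one donor says nothing about another's stool. There are also general safeguards. The second FMT is optional and, in the colonoscopy/sigmoidoscopy item, left to the physician's judgement (the enema item appears to have lost a word there). The exclusion list also lets the physician exclude anyone for whom treatment may pose a health risk. Procedure-form items would not normally confirm eligibility, so their silence on diet is weak evidence. Finally, the missing appendices may settle the matter.

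Much of this stands as mitigation. A per-unit check can be inferred, the form count proves little by itself, and nothing here shows that no diet check exists. It does not remove the conflict. The preceding sentence in VII-B says that patients with inflammatory bowel disease are excluded, and this matches an unconditional criterion, so a reader has no reason to treat the allergy sentence as shorthand. A check held in an appendix would still leave one section excluding patients whom another admits. Physician discretion is not an instruction to check a donor's diet.

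**Conclusion.** The concern holds: the text is wrong as written, at minor severity. The contradiction between Section 6, II and VII-B is certain. The per-unit point holds in a limited form: the available text does not clearly require confirmation for each donor unit. It rests on the supplied text alone and would be answered if the master file or Appendices 2 to 4 already require a per-unit check.

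The documents give no frequency of anaphylactic food allergy, so the number affected among the 150 subjects is not estimated; it is probably very small. The exposure is bounded at one unit without a clearly stated check per affected subject. No endpoint, sample size or planned analysis is altered.

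**What to change.** Keep the conditional rule and state it the same way throughout.

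1. **Section 6, II.** Reword the criterion along these lines: *history of anaphylactic food allergy, unless the allergen is confirmed absent from the donor's diet over the five days before donation for every donor unit the subject receives, any second FMT included; without that confirmation no FMT is given.*
2. **Section 6, IV (both non-response items) and VII-D.** Add that a subject with anaphylactic food allergy receives the second FMT only if the same confirmation is on record for the alternate donor's unit.
3. **VII-B.** Qualify the sentence with the same condition.
4. **Case report form.** Add one line for the confirmation beside the unit or lot number.

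If a per-unit diet check already exists in the master file or appendices, cite it in the criterion.

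The cost is wording in five places (the criterion, two non-response items, VII-B and VII-D), one form line, and one extra diet check for each affected subject who goes on to a second FMT. Occasionally a second FMT will be withheld because the diet cannot be confirmed.

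The alternative is to make the criterion in Section 6, II unconditional. That resolves both points with a single edit, but turns away patients whom the current criterion would admit. Either choice is defensible, provided both sections then say the same thing.
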